1.6 Study Plan

	Between presentation and enrollment day	Screening/ Enrollment day	Per Protocol until discharge (as available)	Hospital Discharge	Day 30
Medical History	x				
Routine Clinical Assessment	x	x	x		
Standard laboratory evaluation	x	x	x		
Inclusion/Exclusion		x			
PCT measurement	x	x	x*		
Document presence or absence of safety endpoints and antibiotic prescription				x	x
Follow-up via chart review/public record: readmission, survival status					x
Follow-up via chart review: Readmission for CDI					x

*PCT measurement only until antibiotics are stopped or patient becomes ineligible

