5 BLOOD SAMPLING

5.1 Collection of specimen

Left over serum from daily routine sampling will be collected in every study patient (intervention and control) and PCT will be measured. Samples should be processed according to clinics' standard operating procedures to gain serum.

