8.4 Analysis Populations

The intention-to-treat (“**ITT**”) patient population will comprise all randomized non-COVID-19 patients.

The per-protocol (“**PP**”) patient population will comprise all ITT patients

- (a) fulfilling study inclusion criteria,
- (b) not meeting study exclusion criteria at enrollment,
- (c) even if meeting study exclusion criterion after enrollment or meeting a pre-defined overruling criterion,

- (d) with PCT measurements performed daily in the first week and thereafter at least every 48 hours during hospitalization and antibiotic treatment,
- (e) if assigned to PCT group, antibiotic steward ship team recommendation given to the treating physician on enrollment day and for each PCT measurement taken Monday-Friday described under d) and antibiotics stopped according to the PCT algorithm. An exception will be made if the stewardship team decides the patient will be given the same recommendation throughout their hospitalization.

Consequently, it should be noted that stewardship team recommendations should also be provided for patients meeting pre-defined overruling criteria (e.g., need for ICU care) since such patients may still qualify for the per-protocol population.

Patients of the PCT arm who are discharged before that day's PCT has resulted will be excluded from the per protocol population. Patients in the PCT arm who were continued on antibiotics despite a weekend/holiday/no stewardship team member available PCT value that would have resulted in an stewardship team recommendation to stop antibiotics will also be excluded from the per protocol population. Patients in the PCT arm whose antibiotics were discontinued despite weekend/holiday/no stewardship team member available PCT value that would have resulted in continuation of antibiotics will also be excluded.

- (f) if assigned to control group, no PCT measurements to treating physician during index hospitalization.

Primary analysis of the superiority endpoint “antibiotic exposure” will be conducted on the basis of the ITT patient population. Analysis of the non-inferiority endpoint “composite adverse events until day 30” will be conducted on the basis of PP and ITT patient population. PP-results will be compared and discussed with corresponding results obtained for ITT patient population.

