2.3.3 Update for Protocol Changes (2022-12-20)

Additional clinical trial simulations were conducted to assess if the specified study design would still be adequate and provide reasonable statistical power when then following study protocol changes were conducted: (a) exchange of primary endpoint and first secondary endpoint (new primary endpoint: shortABx, new first secondary endpoint: CAE30), (b) change of CAE30 inference from superiority to non-inferiority, and (c) change of the times of interim analyses from 500 and 600 patients to 550 and 650 patients, respectively. The simulations were conducted analogously to the ones described in the previous subsection (clinical trial Monte Carlo simulations based on pilot study results) including some improved approximations of data generation according to current study knowledge (blinded analysis results of IA350 data in addition to pilot results: enrollment rate held constant at one patient per day, marginal endpoint rates over both study arms set to 20% for CAE30, 22% for shortABx and 40% for prescribedABx) and of protocol implementation (inclusion of five follow-up days of last enrolled patient at interim analysis according to data transfer experience).

Bayesian CAE30 superiority testing

Probability(CAE30 probability of PCT arm < CAE30 probability of Control arm) > γ

was replaced by CAE30 non-inferiority testing with $M = 10\%$ non-inferiority margin

Probability(CAE30 probability of PCT arm < CAE30 probability of Control arm + M) > γ ,
 $M = 0.1$.

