The protocol changes required a re-specification of the analysis parameter γ to assure type-I error rate control at 2.5% (new order of hierarchical testing of endpoints: first shortABx, then CAE30, then prescribedABx; null hypothesis for shortABx instead of CAE30; interim and final CAE30 NI analyses on PP populations; interim analyses with 550 and 650 patients). Under the null for the primary study endpoint shortABx (relative risk of shortABx for PCT arm versus Control arm set to 1) and under the additional conservative assumptions of effects of CAE30 and prescribedABx as in the pilot study ($RR_{CAE30} = 0.30$, $RR_{prescribedABx} = 0.60$; PCT arm versus Control arm) and the PP population as a random subset of 50% of the patients of the full population (50% estimated for the running study), a γ value of 0.985 was determined to keep the type-I error rate below 2.5% (increase of γ vs. previous protocol version from 0.9785 to 0.985; γ estimated by linear regression of type-I error rate vs. specified γ values based on Monte Carlo runs with 50,000 simulated clinical trials).

Moreover, simulations showed that adequate statistical power could be achieved even for small CAE30 effects. Assuming (a) half of the shortABx effect observed in the pilot study ($RR_{shortABx} = 1.9$), (b) only one tenth of the CAE30 effect observed in the pilot study ($RR_{CAE} = 0.9$), (c) half the prescribedABx effect observed in the pilot study ($RR_{prescribedABx} = 0.80$), and (d) the PP population as a random subset of 50% of the patients of the full population (50% PP patients estimated for the running study), we obtained 99% statistical power for shortABx superiority on ITT population, 75%

for CAE30 non-inferiority on PP population, and 48% for prescribedABx superiority on ITT population. The following Table 2.6 gives an overview of the study design characteristics of this scenario.

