3.1 Analysis Populations

The intention-to-treat (“ITT”) patient population will comprise all randomized non-COVID-19 patients. The per-protocol (“PP”) patient population will comprise all ITT patients (a) fulfilling study inclusion criteria, (b) not meeting study exclusion criteria at enrollment, (c) even if meeting study exclusion criterion after enrollment or meeting a pre-defined overruling criterion, (d) with PCT measurements performed daily in the first week and thereafter at least every 48 hours during antibiotic treatment, (e) ~~-if assigned to PCT group, antibiotic steward~~ ship team recommendation given to the treating physician on enrollment day and for each PCT measurement taken Monday-Friday described under d) and antibiotics stopped according to the PCT algorithm. An exception will be made if the ASP decides the patient will be given the same recommendation throughout their hospitalization.

Consequently, it should be noted that ASP recommendations should also be provided for patients meeting pre-defined overruling criteria (e.g., need for ICU care) since such patients may still qualify for the per-protocol population.

Patients of the PCT arm who are discharged before that day’s PCT has resulted will be excluded from the per protocol population. Patients in the PCT arm who were continued on antibiotics despite a weekend/holiday/no ASP member available PCT value that would have resulted in an ASP recommendation to stop antibiotics will also be excluded from the per protocol population. Patients in the PCT arm whose antibiotics were discontinued despite weekend/holiday/no ASP member available PCT value that would have resulted in continuation of antibiotics will also be excluded.

(f) if assigned to control group, no PCT measurements to treating physician during index hospitalization.

Primary analysis of the superiority endpoint “antibiotic exposure” will be conducted on the basis of the ITT patient population. Analysis of the non-inferiority endpoint “composite adverse events until

day 30" will be conducted on the basis of PP and ITT patient population. PP-results will be compared and discussed with corresponding results obtained for ITT patient population.

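### SAP 3.1(d) lacks the protocol's limit to the hospital stay, so read as written the per-protocol set would lose most patients discharged with antibiotic days remaining

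*SAP*

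**What the plan says.** SAP 3.1(d) makes PP membership conditional on a PCT schedule: "with PCT measurements performed daily in the first week and thereafter at least every 48 hours during antibiotic treatment". Protocol 8.4(d) sets the same schedule with a narrower scope: "with PCT measurements performed daily in the first week and thereafter at least every 48 hours during hospitalization and antibiotic treatment". Neither the SAP version history nor SAP 4.11 lists this difference.

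PCT is an inpatient measurement. Protocol 5.1 states: "Left over serum from daily routine sampling will be collected in every study patient". The study plan in Protocol 1.6 marks PCT up to discharge and leaves it blank at discharge and at Day 30. Its footnote reads: "PCT measurement only until antibiotics are stopped or patient becomes ineligible".

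Antibiotic treatment, by contrast, extends past discharge. SAP 4.1.1 and Protocol 8.2.1 add the days prescribed at discharge to the days in hospital when they define antibiotic duration.

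SAP 4.5 tests CAE30 non-inferiority on PP and repeats it on ITT. Protocol 8.6.4 analyses prescribedABx on ITT first and then on PP.

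**The concern.** A patient discharged on day 3 with four more days of antibiotics is still on treatment in the first week but can have no further PCT. Sampled perfectly in hospital, that patient meets Protocol 8.4(d) and fails SAP 3.1(d) as worded.

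Three things follow if the SAP sentence is programmed as it stands.

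- PP membership would depend largely on whether antibiotics were prescribed at discharge. That is the second secondary endpoint, it arises after randomisation, and the intervention is meant to reduce it. The arms would lose different numbers and kinds of patients.
- The selected set is the one used first for CAE30 non-inferiority, which comes before prescribedABx in the testing hierarchy (SAP 2.4).
- The PP analysis of prescribedABx would have few events, because most patients with the event would have been removed.

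Two programmers, one working from each document, would build different PP sets. SAP version 5 was issued partly to remove ambiguity of this kind.

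**Working it through.** **Who fails under the SAP wording.** In the first week the rule asks for daily PCT, so a patient sent home in that week with antibiotic days remaining fails. After the first week it asks for a PCT at least every 48 hours, so a patient discharged then with no more than about 48 hours of treatment left can still comply. The documents give no discharge days or remaining durations, so the exact share failing cannot be computed. The share discharged on antibiotics is close to an upper limit for pneumonia antibiotics and is used as an approximation below.

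**Share discharged on antibiotics.** SAP 2.3.3 gives "marginal endpoint rates over both study arms set to 20% for CAE30, 22% for shortABx and 40% for prescribedABx", and for the arm difference assumes "half the prescribedABx effect observed in the pilot study", an RR of 0.80.

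- Control: 2 × 0.40 / (1 + 0.80) = 44.4%
- PCT: 0.80 × 44.4% = 35.6%

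Pilot ITT (SAP Table 2.1): PCT 15/47 = 31.9%, control 24/46 = 52.2%, together 39/93 = 41.9%. A figure of about 40%, lower in the PCT arm, is therefore supported as a planning value.

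**The plan's own power figure.** SAP 2.3.3 states 75% for CAE30 non-inferiority on PP. Inputs: PP = 50% of 700, so 175 per arm; CAE30 20% overall with RR 0.9; margin 0.10; γ = 0.985.

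- Control CAE30: 2 × 0.20 / 1.9 = 21.05%; PCT: 0.9 × 21.05% = 18.95%
- SE = √(0.1895 × 0.8105/175 + 0.2105 × 0.7895/175) = 0.0427
- Normal approximation: Φ((0.10 + 0.0211)/0.0427 − 2.170) = 74.6%
- Exact, with Beta(1,1) posteriors and one look: 74.9%

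Both agree with the stated 75%. Interim looks and the preceding shortABx test (stated power 99%) were not modelled.

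**Criterion (d) alone, as worded.** 350 × (1 − 0.356) = 226 PCT and 350 × (1 − 0.444) = 194 control remain, 420 of 700. On this approximation PP could be at most about 60% of patients.

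**Case A: the 50% was estimated without the rule, which is then applied.** Assume the other PP exclusions, and CAE30, are independent of discharge prescribing.

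- PCT: 175 × (1 − 0.356) = 113; control: 175 × (1 − 0.444) = 97
- Exact power at RR 0.9: 53.6% (normal approximation about 51%)
- Exact power with 20% in both arms: 38.5%, against 57.1% at 175 per arm

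**Case B: the 50% already reflects the rule.** PP stays at 350. Split in the ratio 113:97, it is 350 × 113/210 = 188 PCT and 162 control. Exact power at RR 0.9 is 74.9%, unchanged. The unequal, outcome-dependent selection remains.

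**Case C: the protocol's limit applies throughout.** PP stays at 175 per arm and power at about 75%, with no selection on prescribedABx through (d).

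**The case against.** The strongest reply is that the documents already exclude the literal reading. A criterion about keeping to the PCT schedule can only concern the time when PCT is scheduled, and the study plan ends that at discharge. SAP 3.1 separately excludes PCT-arm patients who leave before that day's result is back, which presumes that others who leave can stay in PP. A PP analysis of prescribedABx is planned. SAP 4.11 does not list (d) as a departure from the protocol. This stands as evidence of intent, and it is why the point is minor. It does not make the SAP sentence say what the protocol sentence says.

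It can also be said that Case A needs the 50% to have been estimated under one reading and the final set built under another, and nothing in the documents shows this. That stands too. Independence from CAE30 is also doubtful: patients who die in hospital count as CAE30 events and cannot receive a discharge prescription, so the rule would change the CAE30 rate as well as the sample size.

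A reader might infer three stronger things that the documents do not support.

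- That every patient discharged on antibiotics fails. The exception after the first week rules this out.
- That the pilot PP set, with discharge prescriptions in 7 of 30 PCT and 19 of 29 control patients, would all be excluded, or that it proves which rule applies. Table 2.1 gives counts without durations. Pilot enrolment ended in February 2021, the PP definition was made more precise in SAP version 2 in January 2022, and the documents do not say which definition produced the pilot set.
- That the SAP deleted the phrase. No earlier SAP text is available, and the protocol may have added it.

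**Conclusion.** The two PP definitions differ in a phrase that decides eligibility, and the SAP version, applied as written, would select PP largely on a post-randomisation endpoint. The rest of the documents point to the protocol's rule, so this is a minor inconsistency to correct; they do not show that the analysis will be done the other way.

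The fall in CAE30 power from 75% to about 54% is conditional. It requires Case A, independence of discharge prescribing from the other exclusions and from CAE30, and the planning values of 40% and RR 0.80, which are not arm-specific results of the main trial. Under Case B there is no loss of power, only the selection. It would also be too strong to say that PP alone settles safety, because CAE30 is analysed on ITT as well and the two are compared. The primary endpoint on ITT and all other ITT analyses are untouched.

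**What to change.** In SAP 3.1(d), use the protocol's scope, "at least every 48 hours during hospitalization and antibiotic treatment", and add that antibiotic days after discharge are not considered for criterion (d). State that this definition applies to the interim and the final PP sets, and record the change in the SAP version history. It would help to note there which reading lay behind the 50% PP estimate.

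The cost is one phrase and one sentence in the SAP, with no extra data collection. If any PP set has already been programmed from the SAP wording, it should be rebuilt.

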3.2 Baseline Patient Characteristics

See Section 4.2.

4 Statistical Analysis

4.1 Mathematical Definitions

4.1.1 Short antibiotic treatments ("shortABx", primary endpoint)

will be encoded as the proportion of patients per study arm (PCT arm, control arm) with less than 4 days of antibiotic duration

"antibiotic duration" (third secondary endpoint) is defined as the number of days per patient with antibiotic treatment for pneumonia comprising the number of days of antibiotic treatment during hospitalization ("ABx-days_{hospital}", starting with the first day of PCT measurement which is one day before enrollment into the study, counting all days with antibiotics not marked "not used for pneumonia") and the number of prescribed days of antibiotic treatment at hospital discharge ("ABx-days_{prescribed at discharge}", counting all days with antibiotics marked "to treat pneumonia"). The resulting sum will be bounded up to a maximum follow-up time of 30 days:

$$\text{Antibiotic duration} = \min(30, \text{ABx-days}_{\text{hospital}} + \text{ABx-days}_{\text{prescribed at discharge}})$$

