4.1.2 Composite adverse events until day 30 ("CAE30", first secondary endpoint)

will be encoded as the patient level Boolean inclusive disjunction ("OR") of the following eight binary (true/false) single adverse event endpoints (1a) all-cause in-hospital mortality, (1b) all-cause mortality after discharge (as available), (2) septic shock (vasopressor use for > 1 h), (3) mechanical ventilation (via endotracheal tube for respiratory failure), (4) needed dialysis, (5) lung abscess/empyema/cavitation/necrotizing pneumonia or (6) hospital readmission.

In the case a patient is enrolled with mechanical ventilation, such an event is not considered to be an adverse event due to its occurrence before any intervention. If the patient is then extubated during their hospital stay, re-intubation is only classified as an adverse event if it occurs at least 24 hours post extubation.

In the case a patient is enrolled with septic shock, such an event is not considered to be an adverse event due to its occurrence before any intervention. If the patient then has a resolved septic shock during hospital stay, developing a new septic shock is only classified as an adverse event if it occurs at least 24 hours post resolution of the initial septic shock.

In the case a patient develops a safety adverse event at any point on the day of enrollment post randomization, such an event will be classified as an adverse event.¹

The variable CAE30 mirrors the safety endpoint for pneumonia used in the study ProACT [Huang2018]. And, also as in ProACT, the endpoint will be analyzed in the form of study-arm-specific proportions, see Section 4.3ff.

4.1.3 Antibiotic exposure at discharge (“prescribedABx”, second secondary endpoint) will be encoded as the proportion of patients per study arm (PCT arm, control arm) with antibiotic prescription for pneumonia treatment at discharge from index hospitalization.

The numerical endpoint **antibiotic duration** is the third secondary endpoint, see definition in Section 4.1.1.

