4.4 Primary Analysis of Antibiotic Exposure

The primary endpoint “short antibiotic treatments” will be analyzed for superiority. We will assess the differences in proportions by Bayesian analysis assuming binomially distributed events. Posterior probabilities will be computed study-arm specifically using conjugate beta-distributed and uninformative uniform priors (shape parameters $\alpha = \beta = 1$).

More specifically, the following generative model will be used:

$$\begin{aligned} N_{\text{PCT}}^s &\sim \text{Binomial}(N_{\text{PCT}}, p_{\text{PCT}}) \\ N_{\text{ctrl}}^s &\sim \text{Binomial}(N_{\text{ctrl}}, p_{\text{ctrl}}) \\ \text{priors: } p_{\text{PCT}}, p_{\text{ctrl}} &\sim \text{Uniform}(0, 1) \end{aligned}$$

with

$N_{\text{PCT}}^s, N_{\text{ctrl}}^s$: number of patients with shortABx of the PCT arm and control arm, respectively
 $N_{\text{PCT}}, N_{\text{ctrl}}$: number of patients randomized to the PCT arm and control arm, respectively
 $p_{\text{PCT}}, p_{\text{ctrl}}$: shortABx probability for patients of the PCT arm and control arm, respectively

Differences between beta-distributed study-arm specific posterior probabilities will be computed by Monte Carlo simulation with sampling from study-arm specific posterior probabilities. Success of the analysis of antibiotic exposure is specified by more than 98.5% posterior probability for more frequent short antibiotic treatments in the PCT arm than in the control arm, i.e.,

$$\text{Probability[prob(short-ABx | PCT arm)} > \text{prob(short-ABx | control arm) } > 98.5\%$$

with

$\text{prob(short-ABx | PCT arm)}$: probability of short antibiotic treatment
for patients randomized to the PCT arm,
 $\text{prob(short-ABx | control arm)}$: probability of short antibiotic treatment
for patients randomized to the control arm.

The primary analysis will be conducted based on the ITT population. The analysis will also be conducted based on the PP patient populations and ITT- and PP-results will be compared and discussed.

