4.6 Secondary Analysis of Antibiotic Exposure

The second secondary endpoint “antibiotic exposure at discharge” will be analyzed for superiority. We will assess the differences in proportions by Bayesian analysis assuming binomially distributed events. Posterior probabilities will be computed study-arm specifically using conjugate beta-distributed and uninformative uniform priors (shape parameters $\alpha = \beta = 1$). More specifically, the same generative model will be used as the one for short antibiotic treatments (see Section 4.4). Differences between beta-distributed study-arm specific posterior probabilities will be computed by Monte Carlo simulation with sampling from study-arm specific posterior probabilities. Success of the analysis of antibiotic exposure at discharge is specified by more than $\gamma = 0.985$ posterior probability for less antibiotic exposure of the PCT arm than of the Control arm, i.e., more than $\gamma = 0.985$ probability that prescriptions of antibiotics for pneumonia are less probable for patients of the PCT arm than for patients of the Control arm:

$$\text{Probability[prob(discharge-ABx | PCT arm)} < \text{prob(discharge-ABx | Control arm)} \text{]} > \gamma$$

with

$\text{prob(discharge-ABx | PCT arm)}$: probability of prescribed antibiotics at hospital discharge for patients randomized to the PCT arm,

$\text{prob}(\text{discharge-ABx} | \text{Control arm})$: probability of prescribed antibiotics at hospital discharge for patients randomized to the Control arm,

$$\gamma = 0.985.$$

The endpoints will be tested in a hierarchical manner: first, superiority testing will be conducted for the primary endpoint shortABx (see Section 4.4). If superiority is concluded for shortABx, then non-inferiority testing will be conducted for the first secondary endpoint CAE30 (see Section 4.5). If non-inferiority is concluded for CAE30, then superiority testing will be conducted for the second secondary endpoint prescribedABx. This hierarchical testing scheme allows to test the three endpoints without correction for multiple testing.

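### The primary endpoint shortABx has no survival condition, so a patient who dies with three or fewer antibiotic days is scored as a success; the effect is probably small, and the handling of deaths in prescribedABx is not stated

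*SAP*

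**What the plan says.** SAP 4.1.1, with the same text in Protocol 8.2.1, states that shortABx "will be encoded as the proportion of patients per study arm (PCT arm, control arm) with less than 4 days of antibiotic duration". Duration is the number of in-hospital days with pneumonia antibiotics, "starting with the first day of PCT measurement which is one day" before enrolment, plus the days prescribed at discharge. The only limit is a cap: "The resulting sum will be bounded up to a maximum follow-up time of 30 days".

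The model in SAP 4.4 takes as denominator the "number of patients randomized to the PCT arm and control arm, respectively". The primary analysis is ITT, and by SAP 3.1 that "population will comprise all randomized non-COVID-19 patients".

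SAP 4.1.3 defines prescribedABx as the proportion of patients "with antibiotic prescription for pneumonia treatment at discharge from index hospitalization". SAP 4.6 adds that "the same generative model will be used as the one for short antibiotic treatments", which carries over the randomized denominator.

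Neither document has a rule for death in either endpoint. SAP 4.10 covers missing values by Bayesian imputation but does not say whether a patient who dies in hospital is missing for prescribedABx. The SAP lists ICH E9 (R1) among its guidelines but names no strategy for death as an intercurrent event.

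**The concern.** Death ends antibiotic treatment. In a pure day count, a patient who dies while still being treated, early enough, has a total below 4 and scores the same as a patient whose antibiotics were deliberately stopped. The trial enrols septic patients and recruits from ICU teams, and it asks whether earlier stopping is safe. Its primary efficacy endpoint should not improve when a patient dies.

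shortABx is first in the testing order (SAP 2.4), so no safety test stands in front of it. CAE30 counts deaths against an arm, but it is tested afterwards and primarily on the PP population, while shortABx is judged on ITT.

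For prescribedABx the problem is silence. A patient who dies in hospital has no discharge prescription, and the text leaves open whether that patient counts as not prescribed, is excluded, or is imputed.

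**Working it through.** **Which deaths are affected.** D0 is the day before enrolment and D1 the day of randomization. With daily antibiotics from D0:
- death on D1: 2 days, short;
- death on D2: 3 days, short;
- death on D3: 4 days, not short.

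Only deaths up to about the day after randomization become successes through truncation. A patient who dies later on continuous daily antibiotics is already a failure.

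**Reproducing the plan's power.** SAP 2.3.3 gives a marginal shortABx rate of 22%, RR 1.9, γ = 0.985 and at most 350 per arm. The control rate c solves c(1 + 1.9)/2 = 0.22, so c = 0.152 and the PCT rate is 1.9 × 0.152 = 0.288. With Beta(1,1) priors, each posterior mean is m = (x + 1)/352 and its variance m(1 − m)/353. Success is Φ[(m_PCT − m_ctrl)/√(v_PCT + v_ctrl)] > 0.985. Power at the final look is 98.7–98.8%, against 99% stated. The same approach gives 75.1% for CAE30 non-inferiority with 175 PP patients per arm, against 75% stated.

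**Effect of early deaths on shortABx.** Assumptions, not in the documents: no real effect on duration; base rate b of short treatment equal in both arms, from 10.6% (pilot control, 5/47) to 22%; control early deaths 1%. As written, the success rate in an arm with early-death rate d is d + (1 − d)b. With death coded as not short it is (1 − d)b. Example for b = 0.22: control 0.01 + 0.99 × 0.22 = 0.228; PCT with 3% early deaths 0.03 + 0.97 × 0.22 = 0.243.

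| Excess early deaths, PCT arm | Chance of shortABx success, as written |
|---|---|
| 0 | 1.5% |
| 0.5 points | about 2.2% (2.0–2.3%) |
| 1 point | 2.7–3.4% |
| 2 points | 4.5–7.1% |

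With early deaths coded as not short, the figure for excesses of 1 to 3 points is 0.9–1.3%. These are single-look figures at 350 per arm.

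**Imbalance needed for early deaths to produce success alone.** With 37, 52 or 70 control successes out of 350, the PCT arm needs 57, 75 or 95, that is 20, 23 or 25 more. As a share of 350 this is 5.7 to 7.1 points.

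**Power after recoding.** If equal early deaths of 1–5% are simply removed from both planned rates, power is 98.9–99.6%. If both rates are multiplied by (1 − d), it is 98.7% at d = 1% and 98.2% at d = 5% (0.144 against 0.274).

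**prescribedABx, literal reading.** Assume deaths count as not prescribed, no effect among survivors (40–51% prescribed) and 5% in-hospital deaths in control. With 7.5% or 10% in the PCT arm, the test taken alone succeeds in 2.9–3.5% or 5.3–7.0%; with deaths excluded it stays at about 1.5%. The formal test also needs CAE30 non-inferiority. With control CAE30 at 20% and 5 points of excess mortality, that passes in about 15% (175 per arm) to 28% (350 per arm). The product is about 0.8–2.0%, taking the two as independent.

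**Pilot denominators.** SAP Table 2.1 uses 48/47 (ITT) and 30/30 (PP) for shortABx and CAE30, but 47/46 and 30/29 for prescribedABx, with no reason given.

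**The case against.** The strongest reply on shortABx is that the window is about two days. SAP 4.1 notes, in a footnote, that the algorithm is unlikely to prevent or induce events on the day of randomization. A patient still on antibiotics at death cannot have been harmed by stopping them, and an excess of deaths with no change in antibiotic use has no evident mechanism. The only mortality figures in the documents, 7.4% under standard care and 6.7% under PCT guidance over 30 days (Protocol Appendix E), make a 2-point excess within about a day look large. All of this stands as an argument about size. It does not make the classification right.

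Three stronger readings are tempting, and the documents do not support them:
- **Excess mortality in general favours the PCT arm on shortABx.** It does not; only very early deaths do.
- **prescribedABx counts every in-hospital death as a success.** That is the literal result of SAP 4.1.3 with the denominator in 4.4 and 4.6, but the text never says it, and the smaller pilot denominators may mean that such patients were left out.
- **The pilot denominators show that the SAP is not followed.** The pilot enrolled until 2021-02-24; SAP version 1 is dated 2021-12-13.

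CAE30 is also analysed on ITT, its components are reported, and the DMC receives them by arm. This limits the harm for prescribedABx, whose test comes after CAE30. It leaves the primary endpoint's own definition unchanged. Coding an in-hospital death as exposed at discharge is one debatable estimand choice among several, so it belongs in a sensitivity analysis.

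**Conclusion.** The point holds for shortABx as a classification error in a stated rule: a patient who dies with three or fewer antibiotic days is a primary-endpoint success. The effect is probably small. Under the assumptions above, 0.5 points of excess early death moves the single-look figure from 1.5% to about 2.2%; 1 point takes it above 2.5%. The imbalances are assumed, 2 points is at the high end, and early deaths alone would need a 6–7 point imbalance to produce success. Strictly, this is success for the wrong reason rather than type-I error, because under the written definition the shortABx probability really is higher in the arm with more early deaths.

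For prescribedABx the finding is only that the handling of in-hospital deaths and the denominator are not stated. A bias in its formal test is not established, and the gate through CAE30 would largely contain one.

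**What to change.** In SAP 4.1.1 and Protocol 8.2.1, count as short only patients whose pneumonia antibiotics were stopped, with a total below 4 days, while they were alive. Code death while still on antibiotics before that point as not short. Report the current definition as a sensitivity analysis. A patient who dies after antibiotics were stopped early remains short under this rule; that outcome belongs to CAE30. State the handling of death for the numerical endpoint antibiotic duration as well.

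In SAP 4.1.3 and 4.6, state one denominator for prescribedABx and say whether an in-hospital death is a missing value under SAP 4.10. Explain the 47/46 pilot denominators. Report prescribedABx with in-hospital deaths excluded and with deaths coded unfavourable, both as sensitivity analyses.

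The cost is wording plus a few extra analyses, since survival status and antibiotic start and stop times are already collected (Protocol 7.1). The shortABx rate falls slightly in both arms, with power still about 98–99% for equal early deaths of 1–5%. The change touches the primary endpoint after the 350-patient interim, and γ was set using rates under the current definition. It should therefore be dated and justified before any further unblinded look, with a short check that γ still holds.
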